At the present time, our offices are using outdated communication methods in an age of new technology that include text messaging, smart-phone apps, and social media. Multiple surveys have reported that patients would actually prefer digital communication from their provider. Moreover, physicians have expressed that "professional burnout" is related to excessive paperwork and generalized office inefficiencies. The best available electronic communication is email, but this becomes overbearing for office staff and patients usually have the same predictable questions. Typically, we can predict what types of questions patients will have at their respective time point after surgery.

There has been a recent surge in the development of electronic patient engagement platforms. These new technologies aim to provide patients with a new form of digital communication and optimize our delivery of healthcare information. These digital communication tools are designed to increase patient activation and promote positive patient behavior. There have been a small number of scientific studies that support their efficacy. The reported data suggests that health text messaging is a convenient way for patients to receive information, allows timely distribution of information, increases patient compliance, improves patient outcomes (medication adherence, decrease surgical infections with antiseptic showers), and can reach a large patient population, including those who are socioeconomically isolated.

This has led us to develop our proposed study, which implements an automated unidirectional electronic patient engagement tool that sends patients diagnosis and treatment specific information at the appropriate time to maximize patient outcomes. The program relies on specific SMS text messages that are less than 160 characters; packaged with instructional videos that are less than 30 seconds which demonstrate key points and proper technique for home exercises. The utility of the program is that it anticipates the most common reasons for non-compliance or readmissions in the early (<12 weeks) postoperative period and sends SMS messages to guide patients through this difficult time and prevent additional communication to the office staff and physician. We expect that the results of this study help us understand the utility of text messaging patient instructions in the postoperative period.

Study Rationale

The effect of a digital patient engagement platform will be assessed as it pertains to the improvement in postoperative knee range of motion, office staff efficiency, and patient satisfaction following total joint arthroplasty (TJA) in the form of a total knee arthroplasty (TKA) or total hip arthroplasty (THA).

Hypothesis

The hypothesis is that following the implementation of an electronic digital patient engagement platform will improve the amount of time spent on rehabilitation activities daily, deep vein thrombosis (DVT) compliance, narcotic use, overall mood, save office staff time and resources, and improve patient satisfaction scores in a cohort of patients indicated for TKA or THA.

Study Plan

This study will be a large, prospective trial of patients undergoing TKA or THA. All patients who sign the consent will be enrolled in the study. Enrollment will continue for 150 patients, 75 in each group, where a power analysis will be performed to determine the total number to show a clinically important difference.

Enrollment Process

Patients over 18 who are determined clinically and by knee/hip radiographs to have symptomatic total joint disease, and elect to have surgery will be invited to participate in this study. Informed consent will be obtained preoperatively in the office setting. Only patients recommended to undergo TKA or THA by the treating surgeon will be offered enrollment in the study.

Eligibility

Inclusion Criteria

1. Patient scheduled to undergo a TKA or THA.
2. Written informed consent is obtained

Exclusion Criteria

1. Patients without smartphone capabilities
2. Revision surgery
3. Any patient lacking decisional capability

Study Procedures

- Eligibility - Once a patient has met the pre-operative criteria, s/he will be offered the opportunity to participate in this study.
- Patient Consent - The patient must be made fully aware of the protocol requirements and s/he must acknowledge his/her understanding and agreement by signing the informed consent and privacy statement.
- Text Messaging – 1-84messages will be sent to the patient in the initial 6-week postoperative period between the hours of 9AM and 7PM. Some messages will be associated with Internet links to instructional videos (authorized by the treating physician) for home exercises.

Timeline of Events

1. All patients will have a preoperative knee/hip radiographs.
2. Once informed consent is obtained, the patient will be provided a one-page “diary” with areas to record the amount of time spent on rehabilitation activities daily, overall mood, narcotic use, and DVT prophylaxis compliance.
3. Patients will be randomized to either the control or experimental group. The control group will receive their post-operative instructions in the usual manner. The experimental group will receive their postoperative instruction in the usual manner but will also receive the digital text messages for the initial 6-week postoperative period.
4. If the patient is randomized to the experimental group, we will obtain their preferred cell phone number and this number will be added into the postoperative texting program algorithm.
5. The patient will then undergo surgical reconstruction in the usual manner. The text-messaging program will begin on postoperative day #0.
6. Any phone call or email from patients in the control and experimental treatment groups will be recorded by the surgeon’s office staff for data processing at the completion of the study.

7. The patients will present for the postoperative visits in the standard manner. At the 6-week post-operative visit, the patient will be prompted to return the completed one-page diary.
8. All patients will complete their prescribed physical therapy as determined by the surgeon. The physical therapy protocols will be identical for the control and experiment study cohorts.
9. At their 6-week postoperative visit, the experimental study cohort will be also be asked to fill out a 7 question survey to gather their feedback and satisfaction with the electronic postoperative text messaging program. There will also be a commentary section in the survey to allow them to provide any further recommendations or insight.

Benefits of Participation

There is no direct benefit to the patient for their participation in this study. The results will contribute to the improvement in postoperative care after total joint arthroplasty. The use of this type of electronic patient engagement protocol may improve their recovery and change the way we interact and deliver healthcare information to patients in the future. The study will help determine the extent to which patient enjoy receiving digital information in the postoperative period.

Alternatives to Participation

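### Six hypothesised outcomes with no primary, ranking or success rule, a power analysis tied to none of them, and one outcome (satisfaction) with no control-arm data

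*Combined protocol and SAP*

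**What the plan says.** The Hypothesis states that the messaging program "will improve the amount of time spent on rehabilitation activities daily, deep vein thrombosis (DVT) compliance, narcotic use, overall mood, save office staff time". It counts office resources with staff time, and its sixth item is patient satisfaction scores. It calls none of them primary and does not order them. The document gives no test, significance level or rule for combining results.

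The Study Rationale gives a different list: "improvement in postoperative knee range of motion, office staff efficiency, and patient satisfaction following total joint arthroplasty (TJA". It shares staff efficiency and satisfaction with the Hypothesis in substance. Knee range of motion appears only in the Rationale.

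The Study Plan has the only text on sample size: "Enrollment will continue for 150 patients, 75 in each group, where a power analysis will be performed to determine the total number". The stated aim of that calculation is "to determine the total number to show a clinically important difference", with no outcome and no value attached.

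The Timeline of Events shows what is collected:

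- Item 2: a diary, given to every consenting patient before the randomisation in item 3, covers rehabilitation time, mood, narcotic use and DVT prophylaxis compliance.
- Item 6: "Any phone call or email from patients in the control and experimental treatment groups will be recorded". No counting window is given.
- Item 7: at six weeks "the patient will be prompted to return the completed one-page diary".
- Item 9: "the experimental study cohort will be also be asked to fill out a 7 question survey to gather their feedback and satisfaction" with the texting program.

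**The concern.** A randomised comparison needs a stated outcome, or a stated rule over several outcomes, before its result can be called positive or negative. Here the Hypothesis and the Rationale disagree on the list, so order and emphasis cannot be used to infer a primary.

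Two things follow directly. The 150 patients rest on no named outcome, so nobody can say whether that number is adequate. And nothing in the text stops the outcome that turns out best from being presented as the one that mattered.

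The further consequence depends on the missing success rule. If any favourable result is enough, chance findings of benefit become more frequent. If every outcome must improve, the trial is less likely to succeed than each separate test suggests. If the outcomes are simply described side by side, neither problem arises in that form.

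Satisfaction is a separate matter. An improvement is hypothesised, but no control-arm value will exist to compare it with.

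**Working it through.** **Step 1. Match outcomes to data sources.**

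| Outcome | Source | Both arms? |
|---|---|---|
| Rehabilitation time | Diary, item 2 | Yes |
| DVT compliance | Diary, item 2 | Yes |
| Narcotic use | Diary, item 2 | Yes |
| Mood | Diary, item 2 | Yes |
| Staff time and resources | Calls and emails, item 6 | Yes, by proxy; staff minutes are not recorded |
| Satisfaction | Survey, item 9 | No; experimental arm only, about the texting program |
| Knee range of motion (Rationale only) | None | No measurement step |

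Four outcomes are recorded in both arms as named, and a fifth by proxy. The calculations below use five.

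**Step 2. The plan's own figure.** The total of 150 (75 per arm) can be neither reproduced nor refuted, because no outcome, effect, SD, significance level or power is given. Everything below assumes two-sided 0.05 per test and, where power is needed, 80% for each outcome. Correlations between outcomes are also assumed.

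**Step 3. Any one of five counts as success.** With no true effects and independent tests, the chance of at least one false benefit is 1 − 0.975^5 = 0.119. Counting a significant result in either direction, it is 1 − 0.95^5 = 0.226. For equally correlated normal test statistics:

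| Correlation | False benefit | Either direction |
|---|---|---|
| 0 | 11.9% | 22.6% |
| 0.3 | 10.5% | 20.9% |
| 0.5 | 9.1% | 18.3% |
| Single test | 2.5% | 5% |

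**Step 4. All five must succeed.** With 80% power each and independence, joint power is 0.8^5 = 0.328. At correlation 0.3 it is 0.440, and at 0.5 it is 0.512.

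Mild negative correlation makes both results worse. At −0.2, by simulation, false benefit is 12.3% and joint power is 24%.

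**Step 5. Why the outcome matters for 150.** For a continuous outcome, power is approximately Φ(d × √(75/2) − 1.96), with d in SD units.

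- d = 0.3: Φ(1.837 − 1.96) = 45%.
- d = 0.5: Φ(3.062 − 1.96) = 87%.

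The same 75 per arm is therefore poor or good depending on an effect size that the plan does not give.

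**Step 6. What 75 per arm can detect.** The difference detectable at 80% power is (1.960 + 0.842) × √(2/75) = 0.457 SD, or 0.460 SD by the two-sample t-test. If 80% of diaries return (assumed), 75 × 0.8 = 60 per arm remain. The detectable difference is then 2.802 × √(2/60) = 0.511 SD, or 0.516 SD by the t-test. Power at 0.46 SD falls from 80% to about 71%.

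**The case against.** The best defence is that this is a modest service evaluation. Its introduction hopes to "help us understand the utility of text messaging patient instructions", which fits separate reporting of each outcome with no single verdict. On that reading there is no error rate to inflate, and that stands: the figures in steps 3 and 4 do not apply to it. But the document never calls the study exploratory. It describes a large prospective trial, randomises patients, states a directional hypothesis and refers to a clinically important difference.

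A reader might infer that the deciding outcome can be picked after the fact however the plan is read. The documents do not support that. The Hypothesis joins its outcomes with a conjunction, so requiring all of them to improve is a natural reading. Neither that reading nor separate reporting leaves one deciding outcome to select. The power analysis also lies in the future, so an outcome might still be named then. The supported statement is narrower: no rule is given, and nothing in the text prevents later selection.

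A reader might also infer that the total will be set from the data of the first 150 patients. The power sentence can be read that way, but it does not say so. Nor do the documents show that 150 is too small. They show only that its adequacy cannot be judged.

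The one-arm survey does have a descriptive purpose, since Benefits of Participation mentions learning how far patients enjoy digital information. That justifies collecting it but does not supply the comparison that the Hypothesis asserts.

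**Conclusion.** The concern holds in limited form. From the text alone: there are six unranked outcomes with no primary or success rule, a power sentence tied to no outcome, a satisfaction claim that cannot be tested between arms, and a Rationale outcome that no step measures.

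The size is conditional on a success rule that the plan does not state. An any-one-of-five rule gives a false-benefit rate about four to five times that of a single test (9.1/2.5 = 3.6 to 11.9/2.5 = 4.8). An all-five rule gives joint power of about one third to one half. These figures illustrate the range and are not measured properties of this trial. This should be corrected, but it does not show that the trial is invalid.

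**What to change.** Before any outcome data are seen:

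- **Primary.** Name in the Study Plan one outcome already collected in both arms, and test it once at two-sided 0.05. Two candidates are calls and emails per patient from surgery to the six-week visit, or mean daily rehabilitation minutes from the diary. The first does not depend on diary return.
- **Secondary.** Treat the other both-arm outcomes as secondary. Either test them by Holm's procedure only if the primary is significant, or report them with confidence intervals and no confirmatory claim.
- **Satisfaction.** Report the experimental-arm survey descriptively and remove the claim that satisfaction improves.
- **Knee range of motion.** Reconcile the Rationale with the procedures, either by removing this outcome or by stating how it is measured in TKA patients.
- **Sample size.** State whether 150 is the final total, and give the difference that 75 per arm can detect on the named primary. For a continuous outcome this is about 0.46 SD at 80% power, or about 0.52 SD if 80% of diaries return. A call and email count needs its own calculation on its own scale.

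**Cost.** Most of this is wording, but not all of it. Item 6 needs a counting window. A diary primary means stating a less favourable detectable difference. The alternative, keeping 75 evaluable per arm at 80% return, would need 75/0.8 ≈ 94 per arm (188 in total), and this fix does not ask for that.

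There will also be fewer confirmatory secondary claims. With complete data, a 0.46 SD secondary effect has about 61% power at Holm's strictest step (0.05/4 = 0.0125), before the primary gate. With an 80%-power primary as gate and correlation 0 to 0.5, that falls to about 49-55% if only one secondary is truly affected. It is about 58-63% if all four are equally affected, because Holm's later steps are less strict.

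### No preoperative entry for mood or narcotic use is specified: a minor, cheap gain in precision that cannot be recovered after surgery

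*Combined protocol and SAP*

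**What the plan says.** The Hypothesis section names narcotic use and overall mood among the outcomes expected to improve. Both are captured by the diary in Timeline of Events, item 2, which has "areas to record the amount of time spent on rehabilitation activities daily, overall mood, narcotic use, and DVT prophylaxis compliance".

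The order of events is as follows.
- Enrollment Process: "Informed consent will be obtained preoperatively in the office setting".
- Item 2: the diary is given once consent has been obtained.
- Item 3: "Patients will be randomized to either the control or experimental group".
- Item 5: surgery, with messaging starting on the day of operation.
- Item 7: the diary is returned at the 6-week visit.

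The only preoperative assessment listed is the radiographs in item 1. No date is given for the first diary entry, and the diary form is not reproduced. The document has no analysis section and names no covariate. On sample size, the Study Plan gives 150 patients, 75 per group, "where a power analysis will be performed to determine the total number to show a clinically important difference".

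**The concern.** Mood and narcotic use can both be recorded before surgery, and a patient's preoperative value may predict the postoperative one. Where it does, adjusting the comparison between arms removes part of the variation between patients and narrows the confidence interval. By the order of the listed steps, the patient already holds the diary before surgery, but nothing tells the patient to fill in a line at that point.

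The timing matters more than the size. An analysis section can be written later, but it cannot call on a preoperative value that was never recorded. If the first entry date stays open, some patients may make a preoperative entry and others not, and the covariate would then be only partly available.

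**Working it through.** **What can be reproduced.** The plan gives 75 per arm but no significance level, power, target difference or SD, so there is no power figure to reproduce. Solving backwards with an assumed two-sided 0.05 and 80% power, 75 per arm detects a standardised difference of (1.960 + 0.842) × √(2/75) = 0.457. I use d = 0.46 as the benchmark.

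**Inputs.** From the plan: 75 per arm. Assumed: d = 0.46, two-sided 0.05, one continuous value per patient, no dropout, and a correlation r between the preoperative and postoperative values of 0.1 to 0.6.

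**Unadjusted.** The standardised signal is d × √(n/2) = 0.46 × √37.5 = 2.817. Power = Φ(2.817 − 1.960) = Φ(0.857) = 80.4%.

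**Adjusted for the preoperative line.** The residual variance is multiplied by 1 − r², so the signal becomes 2.817 / √(1 − r²). The equivalent gain in patients is 1/(1 − r²) − 1.

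| r | 1 − r² | Signal | Power | Equivalent extra patients |
|---|---|---|---|---|
| 0.1 | 0.99 | 2.831 | 80.8% | 1% |
| 0.2 | 0.96 | 2.875 | 82.0% | 4% |
| 0.3 | 0.91 | 2.953 | 84.0% | 10% |
| 0.5 | 0.75 | 3.253 | 90.2% | 33% |
| 0.6 | 0.64 | 3.521 | 94.1% | 56% |

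With the t distribution in place of the normal approximation, the figures are 79.9% unadjusted and 80.3%, 81.5%, 83.5%, 89.8% and 93.8% adjusted. The pattern is the same.

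**Joint, for comparison.** The trial admits both procedures ("Patient scheduled to undergo a TKA or THA"). Keep 80.4% as the unadjusted power, assume a 50:50 mix, and let D be the outcome difference between the joints in within-joint SDs. Adjusting for joint then multiplies the signal by √(1 + 0.25 × D²).
- D = 0.2: √1.01, power 80.8%.
- D = 0.5: √1.0625, power 82.7%.
- D = 1.0: √1.25, power 88.3%.

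The document gives no value for D and does not show that the joints differ on any outcome.

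**The case against.** The strongest case against is that the plan made no wrong choice. There is no analysis section, so no unadjusted comparison has been planned, and a preoperative diary entry is not excluded. A randomised comparison without a baseline covariate is valid. Every input behind the power figures is assumed. The plan does not rank its outcomes, so mood or narcotic use may not carry the conclusion. No scale is given for either, and the figures do not transfer directly to a yes/no or count outcome. At correlations of 0.1 to 0.2 the gain is only 1% to 4% in equivalent patients.

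All of this stands, and it is why the point is minor. It does not remove the point: the line costs almost nothing, and the chance to collect it ends at surgery.

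A reader might be tempted by four stronger readings, which the document does not support.
- *The comparison is biased or its error rate inflated.* Allocation is randomised, so a missing baseline value costs precision only.
- *Pooling knee and hip patients without adjustment is a defect in its own right.* The procedure will be known for every patient, so joint can be added when the analysis section is written, before outcome data are seen. Nothing is lost by waiting.
- *Randomisation must be stratified by joint.* Once joint is a covariate, simulation (50:50 mix) shows stratified blocks saving less than 1% of variance. With blocks of 4, 6 and 8, someone who knows the earlier allocations in a stratum could guess about 68% of them, against about 55% with one shuffled list of 75 and 75. Staff do learn the arm: "If the patient is randomized to the experimental group, we will obtain their preferred cell phone number".
- *The same gap applies to every outcome.* Postoperative rehabilitation time and DVT prophylaxis compliance have no direct preoperative counterpart, and the satisfaction survey is given to the experimental arm only. Knee range of motion appears in the Study Rationale ("improvement in postoperative knee range of motion, office staff efficiency, and patient satisfaction") and could have a baseline. However, the Timeline describes no range-of-motion measurement at any time, so that question belongs with the definition of outcomes.

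**Conclusion.** The point holds as a minor, cheap improvement. The plan specifies no preoperative mood or narcotic entry, although the diary is listed before randomisation and surgery. On the assumed benchmark, adjustment raises power from 80.4% to between 80.8% (r = 0.1) and 94.1% (r = 0.6). The true gain is unknown because the correlation, scale, SD and target difference are not given. If most patients report no preoperative narcotic use, the line would add little for that outcome. The point ranks below the absence of a primary outcome and an analysis method, and it needs separate mention only because it is time-critical.

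**What to change.** Add to Timeline of Events, item 2: *When the diary is handed out, and before randomisation, the patient completes one preoperative line for overall mood and current narcotic use, using the same items as the postoperative entries.* Completing it before randomisation means that knowledge of the arm cannot influence the entry.

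In the analysis section, once written, state that the mood and narcotic comparisons are adjusted for this line, and only those. Joint (TKA or THA) can be named there as a further covariate for outcomes measured in both joints and both arms.

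The cost is one diary line and one model term in each of the two analyses, with no extra visit or patient. If the correlation proves weak, the adjustment is close to neutral. Patients who have already had surgery cannot supply the line, so the change is worth most before enrolment starts.

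### The cell number is obtained only after randomisation and only in the experimental arm, so refusals or unusable numbers can surface on one side only; the likely effect is small and nearly free to prevent

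*Combined protocol and SAP*

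**What the plan says.** All references are to the combined protocol and SAP.

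- **Timeline of Events, items 3 and 4.** Item 3 randomises. Item 4 follows: "If the patient is randomized to the experimental group, we will obtain their preferred cell phone number". It is then loaded into the texting software, so it serves to deliver the intervention. No matching step is described for controls.
- **Exclusion Criteria.** "Patients without smartphone capabilities" are excluded whichever arm they would enter. The section does not say how capability is checked.
- **Enrollment Process and Study Procedures.** "Informed consent will be obtained preoperatively in the office setting", and "The patient must be made fully aware of the protocol requirements and s/he must acknowledge his/her understanding and agreement". Both apply to all patients, and the timeline lists consent ahead of randomisation.
- **Study Plan.** "All patients who sign the consent will be enrolled in the study"; no later condition such as a working number is added. The target is given as "Enrollment will continue for 150 patients, 75 in each group", followed by "where a power analysis will be performed to determine the total number to show a clinically important difference".
- **Outcome capture (Timeline of Events, items 6 and 7).** Office contacts are logged for both groups, and the diary is handed back at the 6-week visit. Neither depends on the collected number.

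The document states no analysis population, no intention-to-treat rule and no handling of undelivered texts.

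**The concern.** Owning a smartphone is not the same as supplying a working number and accepting up to 84 messages on it. The eligibility rule covers the first for everyone. The second is settled only for experimental patients, once their allocation is known. The control patient who would also have refused, or whose number would also have failed, is never identified.

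What follows depends on a rule that the plan does not give.

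- **Kept in the experimental arm.** The patient is non-adherent. The randomised comparison is intact, but the estimated effect shrinks and some power is lost.
- **Dropped, or replaced to reach 75.** The experimental arm then contains only patients who can be texted, while the control arm still contains both kinds. If the two kinds differ in outcome, the difference between arms is biased.

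**Working it through.** **The plan's own figure.** The arithmetic 75 + 75 = 150 checks. The 150 cannot be reproduced further, because no alpha, power, effect size, SD or dropout is given and the power analysis is deferred.

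**Inputs.** From the document: 75 per arm. Assumed: two-sided alpha 0.05; outcome SD 1; a fraction *f* of the experimental arm without a usable number, 2%, 5% or 10%; an outcome difference *g* between those patients and the rest, 0.5 SD, with a range of 0.25 to 1.0 SD. The document gives neither *f* nor *g*.

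**Reference effect.** With the normal approximation, the effect detectable with 80% power is (1.960 + 0.842) × √(2/75) = 2.802 × 0.1633 = 0.457 SD. It is a yardstick for the calculation and not a design value of this trial.

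**Case A: kept and analysed as randomised.** The effect becomes 0.457 × (1 − *f*), and power is Φ(effect / 0.1633 − 1.960).

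| *f* | Patients of 75 | Effect (SD) | Power |
|---|---|---|---|
| 0 | 0 | 0.457 | 80.0% |
| 2% | 1.5 | 0.448 | 78.4% |
| 5% | 3.75 | 0.435 | 75.9% |
| 10% | 7.5 | 0.412 | 71.3% |

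The loss is of similar size for other true effects: at *f* = 10%, power goes from 68.8% to 59.7% for 0.40 SD, and from 86.5% to 78.7% for 0.50 SD.

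**Case B: dropped from the experimental arm only.** The full-arm mean equals the retained mean shifted by *f* × *g*, so the bias is *f* × *g*. The standard error is √(1/75 + 1/(75(1 − *f*))). The type I error of a nominal 0.05 test is the two-tailed probability with the statistic shifted by bias / standard error.

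| *f* | Bias at *g* = 0.5 | Bias, *g* = 0.25 to 1.0 | Type I error at *g* = 0.5 | Type I error, *g* = 0.25 to 1.0 |
|---|---|---|---|---|
| 2% | 0.010 SD | 0.005 to 0.020 SD | 0.0504 | 0.0501 to 0.0517 |
| 5% | 0.025 SD | 0.0125 to 0.050 SD | 0.0526 | 0.0507 to 0.0605 |
| 10% | 0.050 SD | 0.025 to 0.100 SD | 0.0602 | 0.0525 to 0.0916 |

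For example, at *f* = 10% and *g* = 0.5, the bias is 0.10 × 0.5 = 0.05 SD. The standard error is √(1/75 + 1/67.5) = 0.168, the shift is 0.05 / 0.168 = 0.298, and the type I error is 0.060.

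The bias flatters the experimental arm if the lost patients would have done worse, and works against it if they would have done better. The document does not say which is likelier.

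**The case against.** A reader might infer that asking one arm only for the number by itself makes the groups non-comparable. The document does not support that. A patient who is never texted is non-adherent, and groups analysed as randomised remain comparable. Bias needs the further act of dropping or replacing such patients, and no section describes it. The Study Plan enrols everyone who signs, and the diary and contact log can be completed without the number. This objection stands. What remains is that the plan does not rule that act out, and that a fixed count of 75 per group leaves room for replacement.

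A second objection is that few patients will be affected. The smartphone exclusion and informed consent both come before randomisation, and someone who agrees to join a texting trial is an unlikely refuser. The number is also requested before surgery, and texting starts on the day of surgery, so a wrong number may be corrected in time. This largely stands and is why low values of *f* are the more plausible. It does not close the gap: the capability check is not described, and consent does not show that a number works. The consent pages are not part of the review copy, so whether they cover agreement to be texted cannot be checked.

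A reader might also infer that moving the step would remove both problems. It would not do so fully. Patients can still block messages, opt out or change phones after allocation, again in one arm only. Only an analyse-as-randomised rule protects the comparison against those events.

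Finally, asking only those who will be texted limits the personal data collected, which is a defensible operational choice. That is a real but small cost to weigh.

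**Conclusion.** The point holds as a minor design improvement; it is neither an error nor a contradiction in the plan. Failures to provide a usable number can appear only after allocation and only in the experimental arm, for a condition that is meant to apply to both.

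The size is unknown and probably small. Over the assumed 2% to 10%, the consequence is either power of 78% to 71% in place of 80%, with a valid comparison, or a bias of 0.01 to 0.05 SD at an assumed 0.5 SD difference. The larger type I error figure, 0.092, needs 10% loss, a full 1.0 SD difference and actual exclusion of those patients together. All of these results rest on assumed rates, an assumed outcome difference and an assumed reference effect. The missing statement of the analysis population decides which of the two cases applies.

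**What to change.** 1. Move the request for the number from Timeline of Events item 4 to the consent step in item 2. Obtain and confirm it for every patient before randomisation, as the practical check of the smartphone exclusion.
2. Keep in item 4 only the activation of the number in the texting program, for patients allocated to the experimental arm.
3. Add a sentence that all randomised patients are analysed in the arm to which they were allocated, whether or not texts were delivered, and that none is replaced after allocation for want of a usable number.

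Step 1 brings most refusals and unusable numbers forward to before allocation and so limits the loss of power. Step 3 prevents exclusion bias from those that remain and from later opt-outs. The enrolment target, outcomes and treatment are unchanged. The cost is one additional personal-data field for control patients who will never be texted, which the privacy statement should cover.
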